6.5 Other exploratory secondary variables

The following variables will also be listed and plotted over time to support the assessment of efficacy as they are components of hematological response (first three) and of complete response (all five).

- Schistocytes
- Platelets
- Erythrocytes
- Proteinuria
- eGFR

6.6 Exploratory objectives

Corporate Confidential Information

6.6.1 Descriptive analyses

Use in the text below of “treatment group” refers to the initially assigned treatment but, if necessary or useful, allows for use of the four treatment sequences that include switching, as described in Section 4.

Corporate Confidential Information

Overlaying plots will be provided over time on study per patient with a colour change to indicate any treatment switch.

7 Statistical methods for safety and tolerability data

7.1.1 Variables

Adverse events, vital signs (blood pressure, pulse rate, body temperature), ECG intervals, laboratory measurements, as well as patient demographics, baseline characteristics, and treatment information are the relevant variables.

7.1.2 Descriptive analyses

Use in the text below of “treatment group” refers to the initially assigned treatment but, if necessary or useful, allows for use of the four treatment sequences that include switching, as described in Section 4.

Patient demographics and other baseline characteristics

All data for background and demographic variables will be listed by treatment group and patient. Summary statistics will be provided by treatment group.

Relevant medical history, current medical conditions, results of laboratory screens, drug tests and any other relevant information will be listed by treatment group and patient.

Treatment

Data for study drug administration and concomitant therapies will be listed by treatment group and patient.

Vital signs

All vital signs data will be listed by treatment group, patient, and visit/time and if ranges are available, abnormalities (and relevant orthostatic changes) will be flagged.

ECG evaluations

All ECG data will be listed by treatment group, patient and visit/time; abnormalities will be flagged.

Clinical laboratory evaluations

All laboratory data will be listed by treatment group, patient, and visit/time and if normal ranges are available, abnormalities will be flagged. A separate listing is provided presenting all parameters in a patient with any abnormal values. Overlaying plots will be provided over time on study per patient with a colour change to indicate any treatment switch.

Adverse events

All information obtained on adverse events will be displayed by treatment group and patient.

The number and percentage of patients with adverse events will be tabulated by body system and preferred term with a breakdown by treatment. A patient with multiple adverse events within a body system is only counted once towards the total of this body system and treatment. Where the duration of an AE spans a switching of treatment, it will only be counted for the treatment in which it initially occurred.

Other safety evaluations

Lansky/Karnofsky scores

Lansky/Karnofsky scores will be listed by treatment group, patient and visit/time along with changes from baseline. Summary statistics (frequency counts) will be provided by treatment group and visit/time. Overlaying plots will be provided over time on study per patient with a colour change to indicate any treatment switch.

Corporate Confidential Information

ADAMST13

All ADAMST13 results will be listed by patient and visit/time.

Transfusions

Information on transfusions will be listed by patient and visit/time.

8 Statistical methods for Biomarker data

Corporate Confidential Information

Handling of LLOQ and ULOQ

Biomarker data are reported as concentration results, measured using a specific assay with a working range defined by the two limits: Lower limit of quantification (LLOQ) and Upper limit of quantification (ULOQ). Values which fall below the LLOQ or above the ULOQ are reported as $< \text{LLOQ} * \text{dilution factor}$ (dilution factor: if sample diluted and concentration measured still below LLOQ) and $> \text{ULOQ} * \text{dilution factor}$, respectively.

To ensure that biomarkers only have numerical values, censored values will be imputed as follows

- Values below the LLOQ are replaced by $\text{LLOQ}/2$.
- Values above the ULOQ are replaced by ULOQ.

Imputed values are used for summary statistics, inferential analyses and plots (with a special symbol). Values below LLOQ and values above ULOQ are shown as such in the listings. In the summary table, the frequency (n, %) of values below the LLOQ and above the ULOQ, respectively, will be included.

If the proportion of imputed data is more than 20% for any treatment group at any time point, a footnote is added to the summary statistics table stating that the proportion of values outside

the limits of quantification is more than 20% for some treatment groups at some time points and that in such cases summary statistics may be heavily biased.

If the proportion of imputed data for a given biomarker, across all treatment groups and time points, is more than 50%, no summary statistics are provided and the data are only listed.

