
First interpretable results (FIR) will not be provided for this trial.

3 Interim analyses

Corporate Confidential Information

4 Statistical methods: Analysis sets

For patients for which the actual first treatment received does not match the randomized treatment then the treatment actually first received will be used for grouping by treatments received.

All patients who receive study drug or SoC and with no protocol deviations with relevant impact on safety will be included in the safety analysis set.

The PK analysis set will include all patients with at least one available valid (i.e. not flagged for exclusion) PK concentration measurement, who received study drug or SoC and who experienced no protocol deviations with relevant impact on PK data.

Corporate Confidential Information

Patients who switch treatments according to the protocol defined rules will be indicated as having received two treatments in the listings, and data from the period after switching will in general be summarized separately if required. Thus in general there may be up to 6 treatment groups in the summary tables:

- LFG316
- SoC
- LFG316 then SoC (in case of switch in treatment)
- SoC then LFG316 (in case of switch in treatment)
- All LFG316 first
- All SoC first

with the first four, mutually exclusive, used in listings, 'by treatment'.

The analysis sets and protocol deviation codes are related as follows:

Table 4-1 Protocol deviation codes and analysis sets

Category Deviation code	Text description of deviation	Data exclusion
Patients are excluded from all (safety) analysis in case of these PDs:		Exclude patient completely from all (safety) analysis sets
I01	ICF not obtained	
Patients are excluded from PK analysis in case of these Protocol Deviations:		Exclude patient from PK analysis set
E11	Patients previously treated with eculizumab for TAM	Unless sufficiently long ago to not affect PK.
Patients are excluded from PD analysis in case of these Protocol Deviations:		Exclude patient from PD analysis set

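### Minor: Section 7.1.2 groups safety data by assigned treatment where Section 4 uses treatment received, and the adverse event table need not cover all LFG316-exposed patients

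*SAP*

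**What the plan says.** Section 7.1.2 specifies the adverse event table in three sentences. The layout is: "The number and percentage of patients with adverse events will be tabulated by body system and preferred term with a breakdown by treatment". The counting unit is: "A patient with multiple adverse events within a body system is only counted once towards the total of this body system and treatment". The rule for events that cross a switch is: "Where the duration of an AE spans a switching of treatment, it will only be counted for the treatment in which it initially occurred".

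The same section opens by defining the term treatment group, which "refers to the initially assigned treatment but, if necessary or useful, allows for use of the four treatment sequences".

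Section 4 (Analysis sets) gives the general scheme. If the first treatment actually received differs from the randomized one, "the treatment actually first received will be used for grouping by treatments received". For switchers, "data from the period after switching will in general be summarized separately if required". It continues: "Thus in general there may be up to 6 treatment groups in the summary tables". The six are *LFG316*, *SoC*, *LFG316 then SoC*, *SoC then LFG316*, *All LFG316 first* and *All SoC first*. The first four are mutually exclusive and are used in listings.

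Section 1.3.2 states the safety objective in terms of LFG316 in patients with TAM. Section 1.4 allows one switch per patient, in either direction.

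**The concern.** There are two separate weaknesses.

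First, the two sections use different grouping rules for the same safety outputs: assignment in 7.1.2, first treatment received in Section 4. They differ only for a patient who started on the treatment to which they were not randomized. For that patient, grouping by assignment would credit adverse events to a treatment that had not been given.

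Second, the safety question is about exposure to LFG316, and a SoC patient who switches is exposed from then on. The available columns are built on first treatment or on sequence, and the columns that would carry events after a switch are left to discretion. A table that complies with the SAP could therefore omit how many exposed patients had an event while on LFG316. The efficacy estimands are only listed (Section 6), so this is one of the few by-treatment summaries left in the reduced analysis.

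**Working it through.** The plan gives no figure to reproduce. The check compares sections and sets, followed by an illustration of scale.

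**Step 1. Grouping rule.** Section 7.1.2 goes by the treatment initially assigned, with the sequences as an option. Section 4 goes by the treatment actually first received when the two differ. They agree for every patient who started as randomized and disagree for every other patient. The SAP does not say how many such patients there were.

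**Step 2. What the onset rule implies.** A rule for events that span a switch has a function only if one patient can count under two treatments. If the columns were assigned arms, or the four mutually exclusive sequences taken over the whole study, each patient would sit in one column and the rule would do nothing. The rule therefore presupposes columns defined by treatment period. Section 4 points the same way by separating post-switch data, but makes this conditional.

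**Step 3. Does any group hold all exposed patients?** Write L and S for never-switched patients on LFG316 and SoC, LS for LFG316 then SoC, and SL for SoC then LFG316. Exposed = {L, LS, SL}.

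| Section 4 group | Contains | Equals exposed set? |
|---|---|---|
| LFG316 | L | no |
| SoC | S | no |
| LFG316 then SoC | LS | no |
| SoC then LFG316 | SL | no |
| All LFG316 first | L, LS | no, omits SL |
| All SoC first | S, SL | no |

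**Step 4. Scale (illustration only).** Section 1.4 gives about 40 planned patients. The SAP gives no allocation ratio, switch counts or event counts, and the trial was terminated. Assume 20 per arm, 6 LFG316-first patients with onset on LFG316, and 3 switchers with onset after moving from SoC to LFG316. Let s be the number of SoC-to-LFG316 switchers.

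- *All LFG316 first*: 6/20 = 30.0%
- *SoC then LFG316*, after the switch: 3/s
- All exposed: (6 + 3)/(20 + s)
- Share of exposed patients outside *All LFG316 first*: s/(20 + s)

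| s | After switch | All exposed | Share omitted |
|---|---|---|---|
| 3 | 3/3 = 100% | 9/23 = 39.1% | 13.0% |
| 5 | 3/5 = 60.0% | 9/25 = 36.0% | 20.0% |
| 10 | 3/10 = 30.0% | 9/30 = 30.0% | 33.3% |
| 15 | 3/15 = 20.0% | 9/35 = 25.7% | 42.9% |

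Against the 30.0% in *All LFG316 first*, the exposed-patient percentage ranges from 9.1 points higher to 4.3 points lower. With s = 0 they are equal.

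The share omitted depends on allocation. For a : 1 (LFG316 : SoC) and switch proportion r among SoC patients it is r/(a + r). With r = 0.15, 0.25, 0.50 and 0.75, a = 1 reproduces the column above; a = 2 gives 7.0%, 11.1%, 20.0% and 27.3%.

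**The case against.** The best defence is that Section 4 already supplies a workable table. It lists groups expressly for summary tables and links the switch groups to data after switching, and the onset rule fits that scheme: events before a switch stay with the first treatment, later ones go to the switch column. If those columns are shown, *All LFG316 first* and *SoC then LFG316* (after the switch) hold different patients, so a reader can add numerators and denominators. With s = 5, 6/20 and 3/5 give 9/25. A pooled column is then a convenience. This largely stands. What it does not remove is the discretion over showing the post-switch columns, or the silence on which period the *All ... first* columns cover.

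On assigned against received, Section 4 is the specific rule for the mismatch case and 7.1.2 a general default that refers back to it. The tabulation sentence also says treatment and not treatment group. That is a fair reading and makes this the weaker part. Even so, the sentence on displaying adverse event information does use the defined term, so the wording should agree.

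Three stronger readings are tempting but unsupported:

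- A reader might infer that the table has no columns or denominators at all. Section 4 largely provides the columns and defines a safety analysis set; only the per-period numbers are unstated.
- A reader might infer that switchers' events would be divided by the first-treatment denominator, giving much larger distortions. No passage suggests a percentage with switchers in the numerator only.
- A reader might extend the point to Section 6.6.1, which has the same defining sentence. Most of the text around it is redacted, so its effect there cannot be judged.

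**Conclusion.** The point holds as a minor one. The two sections state different grouping rules for safety data. No planned group contains all LFG316-exposed patients, and the columns that would let a reader assemble one are optional. The table as specified need not answer the safety objective for everyone exposed.

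The size is conditional. With no switches and no patient started on the wrong treatment there is no effect. Otherwise it depends on counts the SAP does not give; the percentages above rest on assumed arm sizes, switches and events and show scale only. The table is descriptive, with no test or decision attached, and the patient-level listings allow the counts to be rebuilt. The case for a change is that it is cheap and removes a choice that would otherwise be made at programming.

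**What to change.** Amend Section 7.1.2 as follows.

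1. Define treatment group by the treatment actually first received, in line with Section 4, in place of the one initially assigned.
2. Tabulate adverse events by treatment at onset, each denominator being the safety-set patients who received that treatment in that period. *All LFG316 first* and *All SoC first* cover events before any switch. *LFG316 then SoC* and *SoC then LFG316* cover events after the switch and are shown whenever at least one patient switched.
3. Add one column, *Any LFG316*. The denominator is safety-set patients with at least one LFG316 dose; the count is patients with an event starting while on LFG316, whether as first treatment or after a switch. Events starting after a switch from LFG316 to SoC stay in *LFG316 then SoC*, so attribution by onset is kept.

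The cost is a few sentences and one table column. The drawback is that the pooled column mixes first-line exposure with exposure after treatment failure, so it should stand beside the separate columns and not replace them.

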1.4 Study design and treatment

This is a randomized, SoC-controlled, open-label, multi-center study in patients with TAM after hematopoietic precursor cell transplantation (HPCT) from a related or unrelated donor for malignant and nonmalignant disease after myeloablative or non-myeloablative conditioning.

The study will consist of up to 28 days of screening period, 16 weeks treatment period that can be extended to 45 weeks (in case of ongoing symptoms of TAM), 36 weeks follow up, and end of study visit (EOS) at week 52 (Figure 1-1). Duration of follow up will depend on duration of treatment. Patients who are treated for more than 41 weeks will proceed directly to EOS visit.

Figure 1-1

Approximately 40 patients were to be randomized to receive SoC alone or LFG316 plus SoC (excluding plasmapheresis and prohibited treatment). Patients would be included in the study if they have diagnosis of TAM and poor prognostic markers. Corporate Confidential Information

Patients randomized to LFG316 received [redacted] on study days 1, 8, and 15, followed by weekly doses of [redacted] for remaining treatment duration of total 16 weeks.

Patients showing worsening disease (definition below) after two weeks of treatment (day 15) or later until visit at week 3, will be considered failures and could be switched to receive the alternative treatment (SoC or LFG316).

- increasing schistocyte count (+50% or more as compared to baseline),

- and/or increase in erythrocyte or platelet transfusion need (increase of 50% or more in number of transfusions during 2 weeks prior to study visit as compared to number of transfusions needed two weeks before treatment initiation),
- and/or increasing proteinuria (+50% or more as compared to baseline)

Patients showing no response (definition below) between visit at week 4 (day 29) and visit at week 16 were considered to be treatment failures and could be switched to the other treatment arm. Switching the treatment could occur immediately after data is available.

- no decrease in schistocyte count (as compared to baseline)
- and/or continued erythrocyte or platelet transfusion need (less than 25% improvement in number of transfusions during 2 weeks prior to study visit as compared to number of transfusions needed two weeks before treatment initiation)
- and/or non-responding proteinuria (less than 25% reduction in proteinuria compared to baseline)

Patients can only switch study treatment arms once.

2 First interpretable results (FIR)

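### The adverse event table shows only crude patient percentages by treatment, although switching and extension make time at risk unequal; add patient-weeks and first-event rates beside them

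*SAP*

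**What the plan says.** **Adverse event table (SAP Section 7.1.2).** The planned summary is: "The number and percentage of patients with adverse events will be tabulated by body system and preferred term with a breakdown by treatment". The counting rule at a switch is: "Where the duration of an AE spans a switching of treatment, it will only be counted for the treatment in which it initially occurred". Study drug administration is listed by patient. The visible text plans no summary of exposure duration, no patient-time denominator and no common counting window.

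**Time on treatment (SAP Section 1.4).**
- The design has a "16 weeks treatment period that can be extended to 45 weeks (in case of ongoing symptoms of TAM").
- Early switching: "Patients showing worsening disease (definition below) after two weeks of treatment (day 15) or later until visit at week 3, will be considered failures", and these patients may change to the other treatment.
- Later switching: "Patients showing no response (definition below) between visit at week 4 (day 29) and visit at week 16 were considered to be treatment failures", and they may change too.
- The end-of-study visit is at week 52, and "Duration of follow up will depend on duration of treatment".

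**Grouping (SAP Section 4).** Up to six columns are foreseen: the two treatments without a switch, the two switch sequences, and all patients by first treatment. For switchers, "data from the period after switching will in general be summarized separately if required".

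**The concern.** The counting rule charges each treatment with the events that begin on it, but nothing in the table shows how long patients were observed on it. A switch ends the first-treatment period, possibly after about two weeks. Continuing symptoms can extend treatment well past week 16. Both depend on disease course and so may differ between LFG316 and SoC. If they do, two treatments with the same underlying event rate will show different percentages.

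Safety and tolerability is a secondary objective. Section 6 says the efficacy estimands will be listed and not analysed, so the adverse event table is one of the few summaries by treatment that remain. Readers will compare its columns.

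**Working it through.** The SAP states no event rate, so there is no figure to reproduce. The check asks how far crude percentages separate when the true hazards are equal.

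**Inputs from the SAP.** Earliest switch day 15, with the early window running to the week 3 visit; later window week 4 to week 16; treatment 16 weeks, extendable to 45; end of study week 52.

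**Assumed inputs (not in the SAP).** A constant hazard h of 0.005 to 0.3 per week, the same on both treatments; a share s switching at week 3; a share e extended to 45 weeks; the rest treated for 16 weeks. Deaths and withdrawals are ignored.

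**Step 1: percentage for a group, events counted on first treatment only.**

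P = 1 − [s·exp(−3h) + e·exp(−45h) + (1 − s − e)·exp(−16h)]

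Larger imbalance at h = 0.02, where exp(−0.06) = 0.942, exp(−0.90) = 0.407 and exp(−0.32) = 0.726:
- Group A (s = 10%, e = 30%): 1 − (0.1 × 0.942 + 0.3 × 0.407 + 0.6 × 0.726) = 34.8%
- Group B (s = 50%, e = 10%): 1 − (0.5 × 0.942 + 0.1 × 0.407 + 0.4 × 0.726) = 19.8%

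The gap is 15.0 points with no difference in hazard.

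**Step 2: range of hazards** (percent with an event; gaps taken before rounding).

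| h per week | Modest: 10% vs 30% switch, 20% vs 10% extended | Gap | Larger: 10% vs 50% switch, 30% vs 10% extended | Gap |
|---|---|---|---|---|
| 0.005 | 9.6 vs 7.1 | 2.5 | 10.8 vs 5.8 | 5.0 |
| 0.01 | 17.9 vs 13.4 | 4.5 | 20.0 vs 11.0 | 9.0 |
| 0.02 | 31.6 vs 24.1 | 7.5 | 34.8 vs 19.8 | 15.0 |
| 0.05 | 57.8 vs 46.2 | 11.7 | 61.3 vs 37.9 | 23.3 |
| 0.1 | 78.2 vs 65.6 | 12.7 | 80.1 vs 54.8 | 25.4 |
| 0.3 | 95.4 vs 87.3 | 8.0 | 95.4 vs 79.3 | 16.1 |

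If s and e are the same in both groups, the gap is 0 at every hazard. If switching happens at week 8 instead, the gaps shrink to 1.7 to 7.9 points (modest) and 3.5 to 15.7 points (larger).

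**Step 3: events counted through follow-up to week 52.** Every non-switcher then has 52 weeks whether or not treatment was extended, so e drops out. Switchers still lose their first-treatment time at week 3. At h = 0.02, with 1 − exp(−0.06) = 5.8% and 1 − exp(−1.04) = 64.7%:
- 10% switching: 0.1 × 5.8 + 0.9 × 64.7 = 58.8%
- 50% switching: 0.5 × 5.8 + 0.5 × 64.7 = 35.2%

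So a longer counting window removes the effect of extension but not the effect of switching.

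**Step 4: what a rate does.** Divide patients with a first event by patient-weeks up to the first event or the end of the period. Under a constant hazard the expected patient-weeks per patient are P/h: in Step 1, 0.348/0.02 = 17.4 for A and 0.198/0.02 = 9.9 for B. The rate is 2.0 per 100 patient-weeks in both. The denominator must stop at the first event. With full period length instead (mean 23.4 and 12.4 weeks), the figures would be 34.8/23.4 = 1.49 and 19.8/12.4 = 1.60.

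**The case against.** - **Treatment time is not necessarily time at risk.** The SAP states no counting window, which may properly sit in the protocol. If events are counted to week 52, patients treated for 16 and for 45 weeks are observed for about the same time. This stands: the extension contrast is conditional. It does not rescue switchers' first-treatment time (Step 3).
- **Single-patient extremes are not treatment effects.** At h = 0.05, a patient observed for 2, 16 or 45 weeks has a 9.5%, 55.1% or 89.5% chance of an event. A reader might infer that whole treatments could differ that much. The SAP does not support this: groups mix durations, switching can come as late as week 16, and the gap is zero when patterns match. Nor does the SAP show which arm would lose more patients to switching, so no direction of bias can be claimed.
- **The column scheme already helps.** Among the sequence columns in Section 4, the plain LFG316 and SoC columns hold non-switchers, so an early switch does not shorten them. This stands for those two columns. The two switch-sequence columns have a shortened first period by construction. The counting rule also points to a breakdown by period, which makes time on each treatment matter.
- **Rates do not restore comparability.** Switchers are selected for worsening or non-response, and a constant hazard may not hold: if events cluster early, short periods give inflated rates. This stands. It is a reason to show rates beside the percentages and with a caveat, not in their place.
- **Little depends on it.** The table is descriptive, about 40 patients were planned, the study was terminated, and adverse events and dosing are listed by patient. This stands and sets the severity.

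**Conclusion.** The concern holds as a minor point. The table reports numbers and percentages without time at risk, under a rule that assigns events to the treatment on which they began, in a design where time on treatment varies with disease course. Nothing in the SAP is false or contradictory here: number and percent of patients is a properly defined summary, but an incomplete one.

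Under equal constant hazards, and with counting limited to the first treatment, the distortion between treatments runs from zero (matching patterns) through about 2.5 to 13 points (modest imbalance) to about 5 to 25 points (larger imbalance). These figures rest on assumed hazards and on assumed switching and extension shares. No formal test or decision rule is affected, only how the columns are read.

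**What to change.** Keep the crude number and percentage. For each treatment period, add:
1. the number of patients entering the period;
2. total patient-weeks at risk, from the start of that treatment to the switch or to the end of the adverse event counting period, with that end stated in the table;
3. patients with a first event per 100 patient-weeks, the denominator stopping at the first event, at least for any adverse event and by body system.

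Add a footnote that the rates assume a roughly constant hazard, are imprecise in few patients, and do not remove the selection of switchers by disease course.

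The cost is a few extra columns built from dosing, switch and event onset dates. No new data are needed. The downside is that rates by body system will be unstable in a small terminated study, so they should be read as context for the percentages.

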1.3.2 Secondary Objectives

- To assess the safety and tolerability of LFG316 in patients with TAM
- To describe the pharmacokinetics of total LFG316
- To evaluate non-relapse mortality in TAM patients treated with LFG316 as compared to patients on SoC
- To assess complete response rate at 17 weeks in TAM patients treated with LFG316 compared to patients receiving standard of care

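### The AE frequency table counts an event that spans a treatment switch only under the treatment at onset, even if it worsens, becomes serious or is fatal after the switch

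*SAP*

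**What the plan says.** Safety is a stated secondary objective (SAP Section 1.3.2): "To assess the safety and tolerability of LFG316 in patients with TAM". The AE table is specified in Section 7.1.2: "The number and percentage of patients with adverse events will be tabulated by body system and preferred term with a breakdown by treatment". Within a body system and treatment, a patient counts once. For an event that is ongoing when the patient changes treatment, the same section says: "Where the duration of an AE spans a switching of treatment, it will only be counted for the treatment in which it initially occurred".

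Three other provisions bear on this.

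- **AE listing (Section 7.1.2):** "All information obtained on adverse events will be displayed by treatment group and patient".
- **Meaning of treatment group (Section 7.1.2):** the term "refers to the initially assigned treatment but, if necessary or useful, allows for use of the four treatment sequences that include switching".
- **Grouping (Section 4):** up to six groups may appear in summary tables, "with the first four, mutually exclusive, used in listings, 'by treatment". One of those four is the sequence SoC then LFG316. Section 4 also lets post-switch data be summarized separately where this is required.

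On why patients switch, Section 1.4 says that those who worsen early "will be considered failures and could be switched to receive the alternative treatment (SoC or LFG316". Patients without a response between week 4 and week 16 may also switch. Each patient may switch once.

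**The concern.** Attribution by onset is a common convention and works well for an event that carries on unchanged across a switch. It works less well when the clinically important part of the event happens on the second treatment. The word *only* in the counting rule rules out a second count, and Section 7.1.2 provides no other AE table in which deterioration after the switch would be visible by treatment.

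This is more than a corner case, because Section 1.4 selects switchers for a poor course. The early criteria are rises of 50% or more in schistocytes, transfusion need or proteinuria. The later ones are lack of improvement in the same measures. Such patients can be expected to carry ongoing events across the switch, and some of these events may deteriorate afterwards.

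The table also carries weight in this reduced SAP. Section 6 says that the efficacy estimands are listed and not analysed, so the AE frequency table is one of the few by-treatment summaries left. What is at stake is whether a reader of that table can see that an event deteriorated on a given treatment.

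**Working it through.** The SAP states no figure that depends on this rule, so there is nothing to reproduce. The check is to follow single events through the rule. It assumes that the table separates the two treatments of a patient who switches. The counting rule itself presupposes this, since it would have no purpose otherwise.

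| Course of the event | First treatment, current rule | Second treatment, current rule | Second treatment, proposed rule |
|---|---|---|---|
| A. Starts on SoC, continues unchanged on LFG316, one record | 1 | 0 | 0 |
| B. Starts on SoC, worsens, becomes serious or is fatal on LFG316, one record | 1 | 0 | 1 |
| C. As B, but the worsening is entered as a new AE record after the switch | 1 | 1 | 1 |
| D. Starts on LFG316, worsens, becomes serious or is fatal on SoC, one record | 1 | 0 | 1 |

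Four things follow.

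1. A and B give the same counts, although only B contains deterioration on LFG316.
2. B and C describe the same clinical course but give different counts. The table therefore depends on how a worsening is recorded, which this SAP does not state and the protocol may settle.
3. D is the mirror of B. Deterioration on SoC is then represented only by the count under LFG316.
4. In all four cases the event is displayed in the AE listing. By the Section 4 grouping, A to C fall under SoC then LFG316. If the Section 7.1.2 default of initially assigned treatment is used instead, they fall under SoC. Section 7.1.2 marks the switch by colour in the laboratory and Lansky/Karnofsky plots but states no such mark for spanning AEs.

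**Illustration, on assumed inputs.** Suppose that 6 patients switch from SoC to LFG316 and k of them have an event of type B. The number of such events counted under LFG316 is 0 of 6 for every k under the current rule, and k of 6 under the proposed one:

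- k = 0: 0/6 = 0%, no difference
- k = 1: 1/6 = 17%
- k = 2: 2/6 = 33%

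Both 6 and k are assumptions, so these figures show how the rule works and do not estimate its effect. The difference in a body-system row may be smaller. A switcher with another AE in that body system that began after the switch is already counted there under LFG316.

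**The case against.** The strongest case on the other side has five parts.

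- **The event is not hidden.** The rule governs counting, and the listing shows all AE information. A reader might infer that an event which turns fatal after the switch never appears under LFG316. The SAP does not support that, because Section 4 provides a listing group whose label names LFG316, and Section 7.1.2 lists drug administration by patient. This stands, and it confines the point to the frequency table. It does not correct the count.
- **The table shows occurrence only.** It has no severity, seriousness or outcome dimension, so a fatal event adds the same single count as a mild one. An event that began on SoC is also rightly counted under SoC. This stands. The point is that no count is made under the second treatment, and the onset count itself is correct.
- **Recording practice may remove the problem.** If a worsening becomes a new AE record, it does not span the switch and is counted under the second treatment. This stands as a condition: the point applies only to events kept as one record.
- **The rule is symmetric.** A reader might infer that it favours LFG316. Case D shows the opposite effect, and the numbers switching each way are unknown. No net bias can be claimed. Nor can it be assumed that the two effects cancel.
- **Separate post-switch summaries are possible under Section 4.** That provision is general and conditional, while the AE rule in Section 7.1.2 is specific and definite. This part has little force.

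It is also fair to say that the study was terminated, that the analysis is descriptive and reduced in scope, and that only about 40 patients were planned.

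**Conclusion.** The point holds in a limited form. For an AE kept as one record, the frequency table attributes the whole event to the treatment at onset, with no provision for worsening, seriousness or death after the switch. This follows from the stated rule and does not depend on any missing text. It can misattribute deterioration in either direction in a safety summary that the SAP retains.

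The size is unknown. It depends on the number of switchers in each direction, on how many of their ongoing events deteriorate, and on whether a worsening is recorded as a new AE. The SAP gives none of these. The effect is nil if no spanning event deteriorates or if every worsening is a new record. With about 40 patients planned in total, one or two events could change a row visibly, but that is a possibility and not an estimate. This is a cheap improvement to a descriptive table. It is not evidence that the safety conclusions would be wrong.

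**What to change.** Amend the adverse-event text of SAP Section 7.1.2 before database lock:

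1. Keep attribution to the treatment at onset for a spanning AE that continues unchanged.
2. Also count a spanning AE under the second treatment when the collected data show that, after the switch, its severity increased, it became serious or it was fatal. Do not add this count where the worsening is already a separate AE record.
3. Where dated changes in severity or seriousness are not collected, apply item 2 to fatal outcomes only and flag the remaining spanning AEs in the listing. Dates of death are needed in any case for the survival variable in Section 6.4.1. Linking a death to an AE record assumes that AE outcome is recorded.
4. Flag every spanning AE in the listing, with the switch date.

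The cost is a few sentences of SAP text and a derived flag, provided that the data can date the change. The downside is that a few events appear under both treatments, so a footnote to the table should say so. The change concerns tabulation only and leaves the switching rules untouched.
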